8.7.2. Clinical Laboratory Parameters

All clinical laboratory parameters and their changes from baseline will be listed, as applicable; any value outside the clinical reference range will be flagged. Separate listings will be provided for any parameter for which there is any individual subject value outside the respective clinical reference range.

Summary tables and boxplots by treatment and timepoint for Parts A and B and by timepoint for Part C will be provided for clinical chemistry, haematology, and coagulation parameters and their changes from baseline, as applicable.

Values recorded as $< x$, $\leq x$, $> x$, or $\geq x$ will be displayed in the listings as recorded. For the derivation of listing flags, all calculations, and presentation in the figures, $< x$ and $\leq x$ values will be set to half of x whereas $> x$ and $\geq x$ values will be set to x .

8.7.3. Vital Signs Parameters

All vital signs parameters and their changes from baseline will be listed; any value outside the clinical reference range will be flagged.

Summary tables and boxplots by treatment and timepoint for Parts A and B and by timepoint for Part C will be provided for all vital signs parameters and their changes from baseline.

8.7.4. 12-lead Electrocardiogram Parameters

All 12-lead ECG parameters and their changes from baseline will be listed; any value outside the clinical reference range will be flagged.

Summary tables and boxplots by treatment and timepoint for Parts A and B and by timepoint for Part C will be provided for all 12-lead ECG parameters and their changes from baseline.

An outlier analysis will be performed for QT interval corrected for heart rate using Fridericia's formula (QTcF). The analysis will include all individual original, repeat, and unscheduled postdose values.

The maximum postdose values will be summarised by treatment for all Parts according to the following categories:

- ≤ 450 ms
- >450 and ≤ 480 ms (all instances flagged in the listing)
- >480 and ≤ 500 ms (all instances flagged in the listing)
- >500 ms (all instances flagged in the listing)

The maximum increases from baseline will be summarised by treatment for all Parts according to the following categories:

- ≤ 30 ms
- >30 and ≤ 60 ms (all instances flagged in the listing)
- >60 ms (all instances flagged in the listing)

8.7.5. Bristol Stool Chart and Faecal Occult Blood Test

All Bristol stool chart and faecal occult blood test data will be listed.

Summary tables by treatment for Parts A and B and by overall for Part C will be provided for all Bristol stool chart and faecal occult blood test data. Additionally, summary tables by treatment and timepoint for Parts A and B and by timepoint for Part C will be provided for all Bristol stool chart scale and faecal occult blood test data.

8.7.6. Other Assessments

Medical history will not be listed.

All other safety and tolerability assessments not detailed in the above sections will be listed only.

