females (based on an increase in total cholesterol [T-CHO] and emperipolesis in the bone marrow in both sexes at ≥ 10 mg/kg/day). In a 2-week GLP oral toxicology study in the dog, the NOAEL of CCI [REDACTED] was 2 mg/kg/day for both males and females, based on: abnormal stools, decreased bodyweight and decreased food consumption at ≥ 4 mg/kg/day; increased blood lipid system parameters (triglycerides, T-CHO, LDL-C, free cholesterol) and deviation enzymes at ≥ 4 mg/kg/day; and histopathological gastrointestinal (GI) changes in 1 female at 4 mg/kg/day (and 1 male and 1 female at 8 mg/kg/day), culminating in the death or early sacrifice of dogs given ≥ 6 mg/kg/day. In a non-pivotal 2-week toxicity study in male mice, the NOAEL of CCI [REDACTED] was 10 mg/kg/day, based on: decreased body weights, cumulative body weight gain, and food consumption at 300 mg/kg/day; increased blood lipid system parameters (T-CHO, HDL-C, LDL-C) at ≥ 30 mg/kg/day; and histopathological changes in the stomach and small intestine at 300 mg/kg/day, culminating in the death or early sacrifice of mice given 300 mg/kg/day.

Toxicokinetic parameters determined from the pivotal 2-week repeat dose studies in rats and dogs are presented in Table 1 and Table 2.

Table 1: Summary of Toxicokinetic Parameters in 2-week Toxicity Study in Rat Given CCI [REDACTED]

Dose level (mg/kg/day)	N (M/F)	Day	Male			Female		
			C _{max} (ng/mL)	T _{max} (h)	AUC _{0-24h} (ng·h/mL)	C _{max} (ng/mL)	T _{max} (h)	AUC _{0-24h} (ng·h/mL)
5	3/3	1	962	0.5	3610	1370	0.5	4910
	3/3	14	1220	0.5	3930	1600	0.5	4780
10	3/3	1	2130	1.0	8620	3220	0.5	12 500
	3/3	14	2010	1.0	8580	3490	0.5	10 700
20	3/3	1	4900	0.5	23 000	6220	0.5	30 200
	3/3	14	5110	0.5	20 900	7990	0.5	27 400
40	3/3	1	7960	0.5	51 600	9600	0.5	56 800
	3/3	14	8890	0.5	48 700	10 600	0.5	59 700

Mean (n = 3); AUC_{0-24h} = area under the concentration-time curve from time 0 to 24 hours; C_{max} = maximum concentration; T_{max} = time of maximum concentration; N (M/F): Number of animals (male/female)

Table 2: Summary of Toxicokinetic Parameters in 2-week Toxicity Study in Dog Given CCI [REDACTED]

Dose level (mg/kg/day)	N (M/F)	Day	Male			Female		
			C _{max} (ng/mL)	T _{max} (h)	AUC _{0-24h} (ng·h/mL)	C _{max} (ng/mL)	T _{max} (h)	AUC _{0-24h} (ng·h/mL)
2	3/3	1	1450	0.8	8020	918	1.3	6000
	3/3	14	1450	0.7	9340	1350	0.8	8500
4	3/3	1	2780	1.7	19 900	2420	1.3	15 000
	3/3	14	3520	0.7	29 400	3120	0.8	19 900
6	3/3	1	4010	1.2	30 500	3820	1.0	27 900

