8.8. Safety Analysis

Safety parameters will be listed and summarised using descriptive statistics. No formal statistical analysis of safety data is planned. Each AE will be coded using the Medical Dictionary for Regulatory Activities.

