3. STUDY ENDPOINTS

3.1. Primary Endpoints

For Parts A and B, the safety and tolerability endpoints are as follows:

- AEs
- body weight
- clinical laboratory evaluations (haematology, clinical chemistry [with the exception of phospholipid-C], urinalysis, coagulation, and faecal occult blood)
- 12-lead ECG parameters
- vital signs (blood pressure, pulse rate, respiratory rate, and oral body temperature)
- Bristol Stool Chart
- physical examinations

For Part C, the DDI (KRP-A218 alone versus co-administered with itraconazole) assessment, the PK endpoints will be the parameters derived from plasma concentrations of CCI on Days 1 and 11, which are as follows:

- area under the concentration-time curve (AUC) from time 0 extrapolated to infinity ($AUC_{0-\infty}$)
- AUC from time 0 to the time of the last quantifiable concentration ($AUC_{0-t_{last}}$)
- C_{max}
- t_{max}
- apparent terminal elimination half-life ($t_{1/2}$)
- apparent total clearance (CL/F)
- apparent volume of distribution during the terminal phase (V_z/F).

Other PK parameters may also be added.

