10. SIGNIFICANT CHANGES FROM THE PROTOCOL-SPECIFIED ANALYSES

There were no significant changes from the protocol-specified analyses.

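### Post-dose body weight, a named primary safety endpoint in Parts A and B, is listed but not summarised in the SAP, contrary to Protocol 8.8

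*SAP*

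**What the plan says.** SAP 3.1 introduces the primary safety list with "For Parts A and B, the safety and tolerability endpoints are as follows" and gives seven items, with body weight second. The same items are secondary endpoints for Part C in SAP 3.2, and Protocol 2.2.1 and 2.2.2 agree.

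For analysis, Protocol 8.8 states: "Safety parameters will be listed and summarised using descriptive statistics". It makes no exception for any safety parameter.

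SAP 8.7.1 to 8.7.5 plan outputs for adverse events, laboratory parameters, vital signs, 12-lead ECG, and stool chart with faecal occult blood. SAP 8.7.6 then closes the section: "All other safety and tolerability assessments not detailed in the above sections will be listed only". SAP 8.3 summarises screening body weight with the demographics. SAP Section 10 states: "There were no significant changes from the protocol-specified analyses".

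**The concern.** A primary endpoint would normally have at least a descriptive summary by treatment. Here the SAP does more than leave out a detail. It states a rule, listing only, that conflicts with the protocol for a named primary endpoint, and it does not flag the difference.

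Weight is numeric, is measured repeatedly and has a placebo comparator in Parts A and B. It also belongs to the group of findings on which the dog NOAEL was based: "abnormal stools, decreased bodyweight and decreased food consumption at ≥ 4 mg/kg/day" (Protocol 1.2), together with gastrointestinal changes. The SAP tabulates stool form and occult blood by treatment and timepoint, but not weight. At stake is whether the study report can describe weight change by dose against placebo, or leaves readers to assemble it from subject listings.

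**Working it through.** There is no stated figure to reproduce, so the check matches each endpoint to its planned output.

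**Step 1. Primary endpoints in SAP 3.1 against planned summaries**

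| Endpoint | Planned post-dose summary | Source |
|---|---|---|
| Adverse events | Yes | SAP 8.7.1 |
| Body weight | None | SAP 8.7.6 |
| Clinical laboratory | 4 of 5 components | SAP 8.7.2, 8.7.5 |
| 12-lead ECG | Yes | SAP 8.7.4 |
| Vital signs | Yes | SAP 8.7.3 |
| Bristol Stool Chart | Yes | SAP 8.7.5 |
| Physical examinations | None | SAP 8.7.6 |

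Four are summarised, one partly and two not at all: 4 + 1 + 2 = 7.

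**Step 2. Could another section cover weight?** SAP 3.1 defines vital signs as blood pressure, pulse rate, respiratory rate and oral temperature, so SAP 8.7.3 does not. SAP 8.3 covers screening only, which precedes dosing and cannot show change. SAP 8.7.2 to 8.7.4 ask for changes from baseline in their listings. SAP 8.7.6 does not, so even the weight listing need not show change.

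**Step 3. Are the data collected?** Yes (Protocol Appendix 6).
- Part A: Day -1 and the end of each residential period.
- Part B: Day -1, once during Days 2 to 13, before the Day 14 dose, and before discharge.
- Part C: Day -1 and repeat weights through the residential period.

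Under SAP 8.1.5 the baseline is the last value before the first dose, which is the Day -1 weight.

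**Step 4. Numbers of subjects**
- Primary endpoint: 48 (Part A) + 40 (Part B) = 88.
- Secondary endpoint: 12 (Part C), with no placebo.
- Part B: 4 × 8 = 32 active and 4 × 2 = 8 placebo. SAP 6.2 already pools placebo across groups.

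**Step 5. Urinalysis.** This gap has a different source. SAP 3.1 names it within "clinical laboratory evaluations (haematology, clinical chemistry [with the exception of phospholipid-C], urinalysis, coagulation, and faecal occult blood", but the SAP 8.7.2 tables "will be provided for clinical chemistry, haematology, and coagulation parameters and their changes from baseline, as applicable". Urinalysis is therefore listed, with out-of-range values flagged, but not tabulated. SAP 8.7.6 plays no part.

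**Step 6. Exposure behind the dog finding.** At 4 mg/kg/day, mean dog AUC0-24h was 15,000 to 29,400 ng·h/mL (Protocol Table 2, both sexes, Days 1 and 14). The cap on predicted individual human exposure is 3930 ng·h/mL (Protocol 3.5, 3.7).
- 15,000 / 3930 = 3.8
- 29,400 / 3930 = 7.5

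**The case against.** Several stronger readings are tempting, and the documents do not support them.

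- **That weight has no summary at all.** Screening weight is tabulated by treatment. What is missing is any post-dose or change-from-baseline table.
- **That a primary endpoint is affected in all 100 subjects.** It is primary for 88. In the 12 subjects of Part C it is secondary and there is no placebo.
- **That the dog data predict weight loss here.** The dog finding arose at mean exposures about 3.8 to 7.5 times the human cap. It explains the interest in weight but does not show that a loss is likely.
- **That physical examination and urinalysis equally need tables.** Both are largely qualitative, and the discharge examination is only symptom-directed, so a by-timepoint table would mix two kinds of examination. Untoward findings can be recorded as adverse events (Protocol Appendix 1) and so reach the by-treatment TEAE tables.
- **That a planned comparison or safety monitoring is lost.** No safety endpoint has a formal comparison. Escalation relies on an interim safety report covering all available assessments (Protocol 3.6), and weight is not a stopping criterion (Protocol 3.7).

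The best remaining defence is procedural. SAP Section 1 says the SAP supersedes the protocol's statistical considerations and identifies only substantial differences, and listing a descriptive item may not count as one. The table shells are also a separate document that was not available. Both points limit how strongly the silence in Section 10 can be criticised. Neither removes the conflict: the SAP says listed only, and a shell containing a weight table would contradict it. With small groups the listings can be read individually, but a modest mean shift across 32 active and 8 placebo subjects is easier to see in a table.

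**Conclusion.** The point holds for body weight. A primary endpoint for 88 planned subjects has no planned post-dose summary, although Protocol 8.8 calls for one and Section 10 declares no significant change. It matters most in Part B, with 14 days of dosing and several on-study weights. In Part A each dose is single and the Day -1 and end-of-period weights are only days apart.

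This is a gap in descriptive reporting that deserves correction. All the weights are still listed, and no inference or subject protection depends on the table. For physical examination and urinalysis, listing only is a reasonable choice that should be declared. The conclusion assumes that the SAP text governs over any unseen table shells, and that enrolment follows the planned group sizes without the optional groups.

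**What to change.** In SAP 8.7.6, add a descriptive table of body weight and change from baseline, by treatment (with pooled placebo) and timepoint for Parts A and B, and by timepoint for Part C. This is the layout SAP 8.7.3 already uses for vital signs, with the SAP 8.1.5 baseline.

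In SAP Section 10, add one line saying that physical examination and urinalysis are listed only and that this departs from Protocol 8.8. Frequency tables for these two are optional.

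The cost is one table shell and a few lines of SAP text. No new data, visits or tests are needed.

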8.7.7. Safety and Tolerability Statistical Methodology

No inferential statistical analyses are planned.

9. INTERIM ANALYSES

No interim analyses are planned.

10. SIGNIFICANT CHANGES FROM THE PROTOCOL-SPECIFIED ANALYSES

There were no significant changes from the protocol-specified analyses.

12. APPENDICES

Appendix 1: Document History

Status and Version	Date of Change	Summary/Reason for Changes
Final Version 1.0	NA	NA; the first version.

NA = not applicable
